4.1.2 Exclusion Criteria

Patients who meet any of the following criteria will be excluded from study entry:

- Pregnant or breastfeeding, or intending to become pregnant during the study or within 3 months after the final dose of alectinib
- Lung cancer
- Patients with one of the following ALK point mutations: I1171X, G1202R, V1180L
- Prior therapy with an ALK inhibitor
- Liver disease characterized by any of the following:
 - Impaired excretory function or synthetic function or other conditions of decompensated liver disease such as coagulopathy, hepatic encephalopathy, hypoalbuminemia, ascites, or bleeding from esophageal varices
 - Acute viral or active autoimmune, alcoholic, or other types of acute hepatitis:

Active viral hepatitis B is defined as having positive hepatitis B surface antigen (HBsAg). Patients with past hepatitis B virus (HBV) infection or resolved HBV infection (hepatitis B core antibody [HBcAb]–HBcAb positive, but negative HBsAg) are eligible only if the HBV DNA test is negative.

Patients positive for hepatitis C virus (HCV) antibody are eligible only if polymerase chain reaction (PCR) is negative for HCV RNA.

- Known HIV infection
- Patients with symptomatic bradycardia

Alectinib—F. Hoffmann-La Roche Ltd

- Patients with symptomatic or unstable brain metastasis
- Patients with primary CNS tumors are allowed
- Malabsorption syndrome or any other condition that would interfere with enteral absorption
- Incomplete recovery from any surgery prior to treatment
- Any other malignancies within 5 years prior to enrollment, except the following:
 - Curative treated basal cell carcinoma of the skin, early gastrointestinal (GI) cancer by endoscopic resection, in situ carcinoma of the cervix, ductal carcinoma in situ, papillary thyroid cancer
 - Any cured cancer that is considered to have no impact on PFS or OS for the current ALK-positive solid tumor
- Any serious medical condition or abnormality in clinical laboratory tests that, in the investigator's judgment, precludes the patient's safe participation in and completion of the study
- History of hypersensitivity to alectinib or any of its excipients

This includes, but is not limited to, patients with galactose intolerance, a congenital lactase deficiency, or glucose-galactose malabsorption

4.2 SCREEN FAILURES

Individuals who do not meet the criteria for participation in this study (screen failure) may qualify for one screening opportunities (for a total of two screenings per individual) at the investigator's discretion. The investigator will *maintain a* record *of* reasons for screen failure (see Section 4.6.1).

4.3 METHOD OF TREATMENT ASSIGNMENT

This is a Phase II, open-label, single-arm study. Patients with both ALK fusion and selected ALK mutations will be enrolled in the study.

The decentralized study design minimizes the need for on-site visits for patients, thus making clinical trials more accessible to patients regardless of location.

Patients can be identified by means of one of the two following enrollment pathways:

- 1. The Precision Enrollment approach offered by FMI. Briefly, when non–lung cancer samples are determined by FMI central testing to be positive for ALK, an FMI medical oncologist will contact the ordering physician (local oncologist) and provide information about the trial. If this is of interest to both the physician and the patient, enrollment procedures will begin.
- Patients with ALK-positive NGS test results obtained outside FMI'S Precision Enrollment may be identified and the local ALK NGS test report will be made available (see Section 4.6.6) and will be assessed by the investigator for eligibility. The study team and Medical Monitor are to be consulted. If ALK positivity is not

accepted per the criteria, prospective FMI testing is required and the patient may be enrolled if assessed to be ALK-positive by FMI.

For sample requirements, see Section 4.6.6 and Appendix 2, Table 3.

For eligible and enrolled patients, the tumor tissue sample must be submitted (see Section 4.6.6 and Appendix 2, Table 3) for retrospective analysis by FMI using the F1CDx assay.

Replacement of patients with ALK-fusion solid tumors assessed according to RECIST v1.1 will be allowed for enrolled patients that have not taken any dose of alectinib.

4.4 STUDY TREATMENT AND OTHER TREATMENTS RELEVANT TO THE STUDY DESIGN

The IMP for this study is alectinib.

4.4.1 Study Treatment Formulation and Packaging

4.4.1.1 Alectinib

Alectinib will be supplied by the Sponsor as a capsule dosage form containing the active ingredient 9-ethyl-6, 6-dimethyl-8-[4-(morpholin-4-yl) piperidin-1-yl]-11-oxo-6, 11-dihydro-5Hbenzo[b]carbazole-3-carbonitrile hydrochloride.

Each capsule contains 150 mg of alectinib (as a free base) along with lactose monohydrate, carboxymethylcellulose calcium, hydroxypropyl cellulose, sodium lauryl sulfate, and magnesium stearate as excipients.

Alectinib will be supplied by the Sponsor as capsules in bottles. Alectinib capsules should be stored in accordance with the storage instructions on the label.

For more information on the formulation and handling of alectinib, see the latest Alectinib Investigator's Brochure.

4.4.2 Study Treatment Dosage, Administration, and Compliance

Alectinib 600 mg (four 150-mg capsules) is to be administered orally BID with food. The capsules should not be opened, and the contents of capsules should not be dissolved.

A missed dose can be taken within 6 hours of the scheduled time. If the time since the missed dose is greater than 6 hours, or if the patient vomits, the patient should wait until the next schedule time and take the next scheduled dose. Patients should not take two doses at the same time to make up a missed dose.

Patient will be treated until disease progression, unacceptable toxicity, withdrawal from treatment, or death. Treatment beyond radiological progression is possible in the event

of isolated lesion progression if, in the investigator's opinion, there is evidence of ongoing clinical benefit.

Refer to the pharmacy manual for detailed instructions on drug preparation, storage, and administration.

Details on treatment administration (e.g., dose and timing) should be noted on the Study Drug Administration electronic Case Report Form (eCRF). Cases of accidental overdose or medication error, overdose, medication error, drug abuse, or drug misuse, along with any associated adverse events, should be reported as described in Section 5.3.5.11.

Guidelines for dose modification and treatment interruption or permanent discontinuation for patients who experience adverse events are provided in Section 5.1.2.

4.4.3 Investigational Medicinal Product Handling and Accountability

The IMP required for completion of this study will be provided by the Sponsor. The study site (i.e., investigator or other authorized personnel [e.g., pharmacist or mHCP]) is responsible for maintaining records of IMP delivery, IMP inventory, IMP use by each patient, and disposition or return of unused IMP, thus enabling reconciliation of all IMP received. See the country-specific operations manual for additional details.

In order to ensure patient anonymization, the Sponsor will ship the IMP to a licensed pharmacy, which could be an independent vendor or the central site pharmacy. The licensed pharmacy will dispense the IMP after investigator's prescription and manage the IMP and associated shipments to the patient's home; the process will be detailed in the country-specific operations manual as per local requirements.

The study site should follow all instructions included with each shipment of IMP. The licensed pharmacy used for the study will acknowledge receipt of IMPs supplied by the Sponsor by returning the appropriate documentation form to confirm the shipment condition and content. Any damaged shipments will be replaced. The depot must confirm that appropriate temperature conditions have been maintained during transit, either by time monitoring (shipment arrival date and time) or temperature monitoring of the IMP. The IMP must be stored in a secure, environmentally controlled, and monitored (manual or automated) area in accordance with the labeled storage conditions, with access limited to authorized staff.

Investigator or delegate will be responsible for coordinating the shipment of IMP to the patient's home prior to the date and time of the visit. Upon delivery, a telemedicine visit with the patient or patient caregiver will be conducted by the investigator or delegate to confirm that appropriate temperature conditions have been maintained during transit and that the IMP was received in good condition (i.e., no damage and unopened) according to the process described in the country-specific operations manual.

Alectinib—F. Hoffmann-La Roche Ltd

Appropriate packaging will be delivered to patients' homes, or as per local regulations, in order to return unused IMP after IMP accountability is performed by an mHCP or at the site, whichever is in agreement with the local requirements. The returned IMP will be stored at the depot until final disposition is confirmed by the study monitor or Sponsor.

4.4.4 Continued Access to Alectinib

The Sponsor will offer continued access to Roche IMP (alectinib) free of charge to eligible patients in accordance with the Roche Global Policy on Continued Access to Investigational Medicinal Product, as outlined below.

A patient will be eligible to receive Roche IMP (alectinib) after completing the study if all of the following conditions are met:

- The patient has a life-threatening or severe medical condition and requires continued Roche IMP treatment for his or her well-being
- There are no appropriate alternative treatments available to the patient
- The patient and his or her doctor comply with and satisfy any legal or regulatory requirements that apply to them

A patient will not be eligible to receive Roche IMP (alectinib) after completing the study if any of the following conditions are met:

- The Roche IMP is commercially marketed in the patient's country and is reasonably accessible to the patient (e.g., is covered by the patient's insurance or wouldn't otherwise create a financial hardship for the patient)
- The Sponsor has discontinued development of the IMP or data suggest that the IMP is not effective for the indication explored in this study
- The Sponsor has reasonable safety concerns regarding the IMP as treatment for the indication explored in this study
- Provision of the Roche IMP is not permitted under the laws and regulations of the patient's country

The Roche Global Policy on Continued Access to Investigational Medicinal Product is available at the following website:

http://www.roche.com/policy_continued_access_to_investigational_medicines.pdf

4.5 CONCOMITANT THERAPY

Concomitant therapy consists of any medication (e.g., prescription drugs, over-the-counter drugs, vaccines, herbal or homeopathic remedies, nutritional supplements) used by a patient in addition to protocol-mandated treatment from 14 days prior to initiation of study drug to the treatment discontinuation visit occurring 28 days after last dose of study drug. All such medications should be reported to the investigator and recorded on the Concomitant Medications eCRF. Details about the product and the

number of doses will be reported for COVID-19 vaccines and for COVID-19 infection mitigation.

4.5.1 Permitted Therapy

The medications and/or treatments below are permitted:

- Premedication with analgesics and/or anti-emetics may be administered at the discretion of the investigator.
- Local therapy (e.g., stereotactic radiotherapy or surgery) may be given in patients with isolated asymptomatic CNS progression (e.g., new CNS oligometastases) after consultation with the Sponsor.
- In certain instances, palliative radiotherapy to bone lesions and for purposes of pain control may be permitted, provided it does not interfere with the assessment of tumor target/non-target lesions, and is considered to be medically necessary by the investigator. The sponsor must be notified if palliative radiotherapy is started.
- If palliative radiation is indicated, palliative radiation may start within 24 hours of the last dose of alectinib, unless, in the judgment of the investigator, patient safety will require a longer washout period prior to palliative therapy. Dosing of alectinib may resume with the resolution of any radiation toxicity to Grade 1 or better.
- Inactivated vaccines are allowed.

4.5.2 Cautionary Therapy

Caution should be exercised when the following are co-administered with alectinib:

• For medications that are substrates of P-gp transported or breast cancer resistance protein transporter, the investigator should carefully assess the risks against benefits when considering concomitant use of alectinib. Alectinib has been shown to have potential for inhibition of those transporters. Substrates with a narrow therapeutic index (e.g., methotrexate, digoxin) should be avoided. If co-administration cannot be avoided, it is recommended that drug levels and/or signs for toxicity are carefully monitored (see Appendix 4).

4.5.3 Prohibited Therapy

Use of the following concomitant therapies (e.g., prescription drugs, over-the-counter drugs, herbal or homeopathic remedies, and nutritional supplements) is prohibited during the study except during follow-up period and for at least 14 days prior to initiation of alectinib treatment, unless otherwise specified. Exceptions to restrictions of the therapies listed below may be made if the rationale is discussed and documented between the investigator and Sponsor's clinical pharmacologist:

• Systemic immunosuppressive drugs, cytotoxic or chemotherapeutic agents

Note: The use of systemic corticosteroids for the management of CNS metastases may be permitted after discussion with the Medical Monitor.

• Additional investigational drug (excluding post-progression during survival follow-up)

- Radiotherapy/radionuclide therapy, except for palliative radiotherapy to bone lesions or for pain control
- If palliative radiation is indicated, alectinib should be interrupted for at least 24 hours before start of radiation treatment

Dosing of alectinib may resume with the resolution of any radiation toxicity to Grade 1 or better.

The list of medication provided above is not necessarily comprehensive. If in doubt, the investigator may consult with the Medical Monitor when prescribing concomitant medications.

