4.7 TREATMENT, PATIENT, AND STUDY DISCONTINUATION

Patients will continue on study treatment until disease progression, discontinuation, withdrawal of consent, or death, whichever occurs first.

Treatment beyond radiological progression is possible in the event of isolated lesion progression if, in the investigator's opinion, there is evidence of ongoing clinical benefit.

In the event of a patient's voluntary withdrawal of consent, the investigator will make a reasonable effort to document the reported reason for consent withdrawal in the eCRF. All efforts will be made to complete the assessments prior to study withdrawal, as detailed in the protocol.

For patients whose status is unclear because they fail to communicate with the study personnel without confirming discontinuation or withdrawal, study personnel will show due diligence by documenting all actions taken to contact the patient (e.g., dates of telephone calls, registered letters, etc.).

Patients will not be considered as lost to follow-up until due diligence has been completed or until the end of the study.

4.7.1 Study Treatment Discontinuation

Patients must permanently discontinue study treatment if they experience any of the following:

- Any medical condition that the investigator or Sponsor determines may jeopardize the patient's safety if he or she continues to receive study treatment
- Investigator or Sponsor determination that treatment discontinuation is in the best interest of the patient
- Pregnancy

Alectinib—F. Hoffmann-La Roche Ltd 65/Protocol BO41929, Version 4

- Use of an anti-cancer therapy not required per protocol
- Symptomatic deterioration attributed to disease progression
- Any event that meets stopping criteria defined in Section 5.1.2

The primary reason for study treatment discontinuation should be documented on the appropriate eCRF. Patients who discontinue study treatment prematurely will not be replaced. Patients with ALK-fusion tumors who are enrolled in the study and do not receive any dose of study treatment will be replaced.

The mHCP will perform a treatment discontinuation visit 28 days after the final dose of alectinib for safety assessments as described in the schedule of activities (see Appendix 1).

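### Read literally, the mandatory stop in Protocol 4.7.1 covers palliative radiotherapy after which 4.5.1 and 4.5.3 let alectinib resume, and it also reaches the local CNS therapy that 4.5.1 permits

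*Protocol*

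**What the plan says.** Protocol 4.5.1 (Permitted Therapy) contains two permissions.

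- CNS: "Local therapy (e.g., stereotactic radiotherapy or surgery) may be given in patients with isolated asymptomatic CNS progression", after consultation with the Sponsor. New CNS oligometastases are the example given. Nothing is said about interrupting or resuming alectinib.
- Palliative: "palliative radiotherapy to bone lesions and for purposes of pain control may be permitted", provided lesion assessment is not disturbed and the investigator judges it necessary. The Sponsor must be notified. Afterwards, "Dosing of alectinib may resume with the resolution of any radiation toxicity to Grade 1 or better".

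Protocol 4.5.3 (Prohibited Therapy) lists "Radiotherapy/radionuclide therapy, except for palliative radiotherapy to bone lesions or for pain control". It then repeats the statement that dosing may resume. Its lead-in applies the ban during the study, outside follow-up, and for at least 14 days "prior to initiation of alectinib treatment, unless otherwise specified". It adds: "Exceptions to restrictions of the therapies listed below may be made if the rationale is discussed and documented" between the investigator and the Sponsor's clinical pharmacologist. Surgery is not on the list.

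Protocol 4.7.1 opens with "Patients must permanently discontinue study treatment if they experience any of the following", and one item is "Use of an anti-cancer therapy not required per protocol". It makes no exemption for therapy permitted elsewhere.

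Protocol 3.1, 4.4.2 and 4.7 allow alectinib beyond radiological progression when an isolated lesion progresses and the investigator sees continuing benefit.

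**The concern.** A stopping criterion should sort patients the same way at every site. Here the test in 4.7.1 is whether the therapy was required, while 4.5.1 and 4.5.3 work by permission. A therapy that is permitted but not required falls between the two: one section mandates a permanent stop and two others describe how to restart.

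Two sites facing the same event could then act differently. What is at stake is treatment duration and exposure first. Beyond that, a patient who has not progressed, receives palliative radiotherapy and is taken off drug under 4.7.1 goes on being followed for PFS (and for DOR, if a responder) without treatment, for a reason that is an accident of wording.

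**Working it through.** There is no stated figure to reproduce. The check is a comparison of text.

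**1. Does permitted radiotherapy meet the 4.7.1 trigger?** Two conditions must hold.

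- *Not required.* Section 4.5.1 uses permissive wording for both therapies. Neither is required anywhere in the protocol.
- *Anti-cancer therapy.* The protocol does not define the term. Elsewhere, though, the documents class radiotherapy as cancer therapy. The inclusion criteria (4.1.1) put the radiotherapy washout under prior cancer therapies. The long-term follow-up footnote in Appendix 1 gives radiotherapy and surgery as examples of further cancer therapies and procedures. SAP 5.7.2 counts both within previous and concomitant cancer therapy.

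A site that applied 4.7.1 to radiotherapy would be reading the text as it stands.

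**2. The sections side by side.**

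| Protocol section | Palliative radiotherapy (bone or pain) | Local CNS therapy |
|---|---|---|
| 4.5.1 | Permitted; dosing may resume | Permitted after Sponsor consultation; dosing not addressed |
| 4.5.3 | Excepted from the ban; dosing may resume | Stereotactic radiotherapy not among the bullet's exceptions; surgery not listed |
| 4.7 | Not addressed | Continuing is possible in isolated lesion progression |
| 4.7.1, read literally | Permanent stop | Permanent stop |

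The palliative column holds an explicit contradiction. In the CNS column the permission to continue is only implied.

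**3. How firm is 4.5.3 on CNS radiotherapy?** The bullet carries over one of the two radiotherapy permissions in 4.5.1 and omits the other, so its list can be taken as complete. The qualifier in the lead-in may refer to 4.5.1, or only to the 14-day period next to it. The documented-exception route is open, but its contact is the Sponsor's clinical pharmacologist, where 4.5.1 names the Sponsor.

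**4. Route to the endpoints.** After a stop without progression, scans continue every 8 weeks until progression (4.6.5, 4.7.1). The PFS and DOR rules (Protocol 6.4.2.1; SAP 5.4.2.1 and 5.4.2.2) have no censoring for stopping drug or for new therapy. A progression after a literal 4.7.1 stop therefore counts as an event on its own date. For new CNS lesions, Appendix 5 already counts progression, so the PFS or DOR event comes before the local therapy. The possible effect is thus confined to patients without progression who receive palliative radiotherapy.

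**5. Size.** The documents give no rate of on-study radiotherapy or CNS local therapy. If 5% to 20% is assumed purely for illustration, then 50 × 0.05 = 2.5 and 50 × 0.20 = 10 of about 50 fusion patients would meet the conflicting text. This range has no anchor in the documents, pools both therapies, and counts patients exposed to the conflict. It does not measure a change in any estimate.

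**6. Timing.** Section 4.5.1 lets palliative radiation begin inside the 24 hours following the last alectinib dose, unless the investigator judges a longer washout necessary. Section 4.5.3 says the drug should be held for no less than 24 hours beforehand. These statements do not agree either.

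**The case against.** The strongest reply is that specific text governs general text. Two sections say in so many words that dosing may resume after palliative radiation, and a sensible site would follow them over a general item in a list. That is probably how many sites would act, so the claim is that patients could be handled differently, not that they would be. But 4.7.1 is phrased as an obligation and nothing says it yields, so the conflict stands.

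A reader might infer that 4.5.3 bans stereotactic CNS radiotherapy outright, so that any site using the 4.5.1 permission commits a deviation. The documents do not support this. The lead-in to 4.5.3 can be read as deferring to 4.5.1, exceptions can be documented, and surgery is not prohibited there. What remains is a missing cross-reference and two different contacts. Both contacts belong to the Sponsor, so this is an ambiguity and not a proven clash.

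A reader might also infer damage to the primary endpoint. Protocol 2.1.1 and SAP Table 2 apply a treatment-policy approach to additional therapy and early discontinuation, and 4.6.5 asks for confirmation of response even after a responder leaves treatment. A stop before the confirming scan could in principle cost a confirmation, but nothing in the documents shows that it would.

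**Conclusion.** The contradiction holds for palliative radiotherapy: 4.7.1, followed literally, takes a patient off drug permanently where 4.5.1 and 4.5.3 both allow dosing to resume. For local CNS therapy the same wording applies, but continuation is only implied by 4.7, and the mismatch with 4.5.3 is softened without being clearly resolved.

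The conclusion rests on two readings: that not required means what it says, and that radiotherapy counts as anti-cancer therapy, as the documents' own usage suggests. The consequence is for treatment duration and exposure. An effect on PFS and DOR is possible only in the subset identified above. It would be tempting to say that those estimates are lowered, but without a rate of such cases or any figure for the effect of stopping, neither its occurrence nor its size can be established. Both endpoints are estimated by Kaplan-Meier without a formal test.

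**What to change.** In one protocol amendment:

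- State in the 4.7.1 criterion whether it includes or excludes the therapies listed in 4.5.1.
- State in the 4.5.3 exception list whether it includes or excludes those same therapies, and cross-refer to 4.5.1.
- Say explicitly what applies to alectinib dosing after local CNS therapy, consistently with 4.7.
- Name one approval route and one contact.
- Reconcile the two statements on timing between the last dose and palliative radiation.

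The sponsor decides which rule stands; no view is taken here on the clinical choice. The cost is a short amendment, with the ethics and, where locally required, regulatory approval that Section 9.7 calls for. The analysis methods in the SAP do not need to change.
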